7.6. Concomitant medications/products and concomitant vaccinations

At each study visit, the investigator should question the subject about any medications/products taken and vaccinations received by the subject.

7.6.1. Recording of concomitant medications/products and concomitant vaccinations

The following concomitant medication(s)/product(s)/vaccine(s) must be recorded in the eCRF.

- All concomitant medications/products, except vitamins and dietary supplements, administered during the period starting within seven days following each dose of study vaccines (Day 0 to Day 6) and during the entire sporozoite challenge (Day 286 to Day 314).
- Any concomitant vaccination administered in the period starting seven days before the first dose of study vaccines and ending at the last study visit (Day -7 to Day 376) and during the entire sporozoite challenge (Day 286 to Day 314).
- Prophylactic medication (i.e. medication administered in the absence of ANY symptom and in anticipation of a reaction to the vaccination).

E.g. an anti-pyretic is considered to be prophylactic when it is given in the absence of fever and any other symptom, to prevent fever from occurring (fever is defined as temperature $\geq 37.5^{\circ}\text{C}/99.5^{\circ}\text{F}$ for oral, axillary or tympanic route, or $\geq 38.0^{\circ}\text{C}/100.4^{\circ}\text{F}$ for rectal route).

- Any concomitant medications/products/vaccines listed in Section 7.6.2.
- Any concomitant medications/products/vaccines relevant to a SAE/pIMD to be reported as per protocol or administered at any time during the study period for the treatment of a SAE /pIMD. In addition, concomitant medications relevant to SAEs and pIMD need to be recorded on the expedited Adverse Event report.

7.6.2. Concomitant medications/products/vaccines that may lead to the elimination of a subject from ATP analyses

The use of the following concomitant medications/products/vaccines will not require withdrawal of the subject from the study but may determine a subject's evaluability in the ATP analysis. See Section 11.5 for cohorts to be analyzed.

- Any investigational or non-registered product (drug or vaccine) other than the study vaccines used during the study period.
- Immunosuppressants or other immune-modifying drugs administered chronically (i.e. more than 14 days in total) during the study period. For corticosteroids, this will mean prednisone ≥ 20 mg/day (for adult subjects), or equivalent. Inhaled and topical steroids are allowed.

- Long-acting immune-modifying drugs administered at any time during the study period (e.g. infliximab).
- A vaccine not foreseen by the study protocol administered during the period starting seven days before each dose and ending seven days after each dose of vaccines administration*.

* In case an emergency mass vaccination for an unforeseen public health threat (e.g.: a pandemic) is organized by the public health authorities, outside the routine immunization program, the time period described above can be reduced if necessary for that vaccine provided it is licensed and used according to its Summary of Product Characteristics or Prescribing Information and according to the local governmental recommendations and provided a written approval of the Sponsor is obtained.

- Immunoglobulins and/or any blood products administered during the study period.
- Drugs known to have anti-*Plasmodium* properties, used during the challenge period before identification of parasitemia.

7.7. Intercurrent medical conditions that may lead to elimination of a subject from ATP analyses

For vaccinated subjects, at each study visit subsequent to the first vaccination/the vaccination visit, it must be verified if the subject has experienced or is experiencing any intercurrent medical condition. If it is the case, the condition(s) must be recorded in the eCRF.

For the infectivity controls group, at each study visit subsequent to the sporozoite challenge visit, it must be verified if the subject has experienced or is experiencing any intercurrent medical condition. If it is the case, the condition(s) must be recorded in the eCRF.

Subjects may be eliminated from the ATP cohort for analysis of immunogenicity and efficacy if, during the study, they incur a condition that has the capability of altering their immune response or are confirmed to have an alteration of their initial immune status.

8. HEALTH ECONOMICS

Not applicable

9. SAFETY

The investigator or site staff is/are responsible for the detection, documentation and reporting of events meeting the criteria and definition of an AE or SAE as provided in this protocol.

Each subject will be instructed to contact the investigator immediately should the subject manifest any signs or symptoms they perceive as serious.

9.1. Safety definitions

9.1.1. Definition of an adverse event

An AE is any untoward medical occurrence in a clinical investigation subject, temporally associated with the use of a medicinal product, whether or not considered related to the medicinal product.

An AE can therefore be any unfavorable and unintended sign (including an abnormal laboratory finding), symptom, or disease (new or exacerbated) temporally associated with the use of a medicinal product. For marketed medicinal products, this also includes failure to produce expected benefits (i.e. lack of efficacy), abuse or misuse.

Examples of an AE include:

- Significant or unexpected worsening or exacerbation of the condition/indication under study.
- Exacerbation of a chronic or intermittent pre-existing condition including either an increase in frequency and/or intensity of the condition.
- New conditions detected or diagnosed after investigational vaccines administration even though they may have been present prior to the start of the study.
- Signs, symptoms, or the clinical sequelae of a suspected interaction.
- Signs, symptoms, or the clinical sequelae of a suspected overdose of either investigational vaccines or a concurrent medication (overdose per se should not be reported as an AE/SAE).
- Signs, symptoms temporally associated with vaccines administration.
- Pre- or post-treatment events that occur as a result of protocol-mandated procedures (i.e. invasive procedures, modification of subject's previous therapeutic regimen).

AEs to be recorded as endpoints (solicited AEs) are described in Section 9.1.3. All other AEs will be recorded as UNSOLICITED AEs.

Examples of an AE DO NOT include:

- Medical or surgical procedures (e.g. endoscopy, appendectomy); the condition that leads to the procedure is an AE/SAE.
- Situations where an untoward medical occurrence did not occur (e.g. social and/or convenience admission to a hospital, admission for routine examination).
- Anticipated day-to-day fluctuations of pre-existing disease(s) or condition(s) present or detected at the start of the study that do not worsen.
- Pre-existing conditions or signs and/or symptoms present in a subject prior to the first study vaccination. These events will be recorded in the medical history section of the eCRF.

9.1.2. Definition of a serious adverse event

A SAE is any untoward medical occurrence that:

- a. Results in death,
- b. Is life-threatening,

Note: The term ‘life-threatening’ in the definition of ‘serious’ refers to an event in which the subject was at risk of death at the time of the event. It does not refer to an event, which hypothetically might have caused death, had it been more severe.

- c. Requires hospitalization or prolongation of existing hospitalization,

Note: In general, hospitalization signifies that the subject has been admitted at the hospital or emergency ward for observation and/or treatment that would not have been appropriate in the physician’s office or in an out-patient setting. Complications that occur during hospitalization are also considered AEs. If a complication prolongs hospitalization or fulfills any other serious criteria, the event will also be considered serious. When in doubt as to whether ‘hospitalization’ occurred or was necessary, the AE should be considered serious.

Hospitalization for elective treatment of a pre-existing condition (known or diagnosed prior to informed consent signature) that did not worsen from baseline is NOT considered an AE.

- d. Results in disability/incapacity, OR

Note: The term disability means a substantial disruption of a person’s ability to conduct normal life functions. This definition is not intended to include experiences of relatively minor medical significance such as uncomplicated headache, nausea, vomiting, diarrhea, influenza like illness, and accidental trauma (e.g. sprained ankle) which may interfere or prevent everyday life functions but do not constitute a substantial disruption.

- e. Is a congenital anomaly/birth defect in the offspring of a study subject.

Medical or scientific judgment should be exercised in deciding whether reporting is appropriate in other situations, such as important medical events that may not be immediately life-threatening or result in death or hospitalization but may jeopardize the subject or may require medical or surgical intervention to prevent one of the other outcomes listed in the above definition. These should also be considered serious. Examples of such events are invasive or malignant cancers, intensive treatment in an emergency room or at home for allergic bronchospasm, blood dyscrasias or convulsions that do not result in hospitalization.

9.1.3. Solicited adverse events

9.1.3.1. Solicited local (injection-site) adverse events

The following local (injection-site) AEs will be solicited:

Table 22 Solicited local adverse events

All age groups
Pain at injection site
Redness at injection site
Swelling at injection site

9.1.3.2. Solicited general adverse events

The following general AEs will be solicited:

Table 23 Solicited general adverse events

Adult
Fatigue
Fever
Gastrointestinal symptoms †
Headache

† Gastrointestinal symptoms include nausea, vomiting, diarrhea and/or abdominal pain.

Note: Temperature will be recorded in the evening. Should additional temperature measurements be performed at other times of day, the highest temperature will be recorded in the eCRF.

9.1.4. Clinical laboratory parameters and other abnormal assessments qualifying as adverse events or serious adverse events

In absence of diagnosis, abnormal laboratory findings (e.g. clinical chemistry, hematology, urinalysis) or other abnormal assessments that are judged by the investigator to be clinically significant will be recorded as AE or SAE if they meet the definition of an AE or SAE (refer to Sections 9.1.1 and 9.1.2). Clinically significant abnormal laboratory findings or other abnormal assessments that are present at baseline and significantly worsen following the start of the study will also be reported as AEs or SAEs.

The investigator will exercise his or her medical and scientific judgment in deciding whether an abnormal laboratory finding or other abnormal assessment is clinically significant.

9.1.5. Adverse events of specific interest

AEs of specific interest for safety monitoring include meningitis and pIMDs.

9.1.5.1. Potential immune-mediated diseases

pIMDs are a subset of AEs that include autoimmune diseases and other inflammatory and/or neurologic disorders of interest which may or may not have an autoimmune etiology. AEs that need to be recorded and reported as pIMDs include those listed in [Table 24](#).

However, the investigator will exercise his/her medical and scientific judgment in deciding whether other diseases have an autoimmune origin (i.e. pathophysiology involving systemic or organ-specific pathogenic autoantibodies) and should also be recorded as a pIMD.

Table 24 List of potential immune-mediated diseases

Neuroinflammatory disorders	Musculoskeletal disorders	Skin disorders

 • Cranial nerve disorders, including paralyses/paresis (e.g. Bell's palsy) • Optic neuritis • Multiple sclerosis • Transverse myelitis • Guillain-Barré syndrome, including Miller Fisher syndrome and other variants • Acute disseminated encephalomyelitis, including site specific variants: e.g. non-infectious encephalitis, encephalomyelitis, myelitis, myeloradiculoneuritis • Myasthenia gravis, including Lambert-Eaton myasthenic syndrome • Immune-mediated peripheral neuropathies and plexopathies, (including chronic inflammatory demyelinating polyneuropathy, multifocal motor neuropathy and polyneuropathies associated with monoclonal gammopathy). • Narcolepsy 	
 • Systemic lupus erythematosus and associated conditions • Systemic scleroderma (Systemic sclerosis), including diffuse systemic form and CREST syndrome • Idiopathic inflammatory myopathies, including dermatomyositis • Polymyositis • Antisynthetase syndrome • Rheumatoid arthritis, and associated conditions including juvenile chronic arthritis and Still's disease • Polymyalgia rheumatica • Spondyloarthritis, including ankylosing spondylitis, reactive arthritis (Reiter's Syndrome) and undifferentiated spondyloarthritis • Psoriatic arthropathy • Relapsing polychondritis • Mixed connective tissue disorder 	
 • Psoriasis • Vitiligo • Erythema nodosum • Autoimmune bullous skin diseases (including pemphigus, pemphigoid and dermatitis herpetiformis) • Alopecia areata • Lichen planus • Sweet's syndrome • Localised Scleroderma (Morphoea)

Vasculitides	Blood disorders	Others

 Large vessels vasculitis including: giant cell arteritis such as Takayasu's arteritis and temporal arteritis. Medium sized and/or small vessels vasculitis including: polyarteritis nodosa, Kawasaki's disease, microscopic polyangiitis, Wegener's granulomatosis, Churg–Strauss syndrome (allergic granulomatous angiitis), Buerger's disease (thromboangiitis obliterans), necrotizing vasculitis and anti-neutrophil cytoplasmic antibody (ANCA) positive vasculitis (type unspecified), Henoch-Schonlein purpura, Behcet's syndrome, leukocytoclastic vasculitis. 	
 Autoimmune hemolytic anemia Autoimmune thrombocytopenia Antiphospholipid syndrome Pernicious anemia Autoimmune aplastic anaemia Autoimmune neutropenia Autoimmune pancytopenia 	
 Autoimmune glomerulonephritis (including IgA nephropathy, glomerulonephritis rapidly progressive, membranous glomerulonephritis, membranoproliferative glomerulonephritis, and mesangioproliferative glomerulonephritis) Ocular autoimmune diseases (including autoimmune uveitis and autoimmune retinopathy) Autoimmune myocarditis/cardiomyopathy Sarcoidosis Stevens-Johnson syndrome Sjögren's syndrome Idiopathic pulmonary fibrosis Goodpasture syndrome Raynaud's phenomenon
Liver disorders	Gastrointestinal disorders	Endocrine disorders

 Autoimmune hepatitis Primary biliary cirrhosis Primary sclerosing cholangitis Autoimmune cholangitis 	
 Inflammatory Bowel disease, including Crohn's disease, ulcerative colitis, microscopic colitis, ulcerative proctitis Celiac disease Autoimmune pancreatitis 	
 Autoimmune thyroiditis (including Hashimoto thyroiditis) Grave's or Basedow's disease Diabetes mellitus type I Addison's disease Polyglandular autoimmune syndrome Autoimmune hypophysitis

When there is enough evidence to make any of the above diagnoses, the AE must be reported as a pIMD. Symptoms, signs or conditions which might (or might not) represent the above diagnoses, should be recorded and reported as AEs but not as pIMDs until the final or definitive diagnosis has been determined, and alternative diagnoses have been eliminated or shown to be less likely.

In order to facilitate the documentation of pIMDs in the eCRF, a pIMD standard questionnaire and a list of preferred terms and preferred terms codes corresponding to the above diagnoses will be available to investigators at study start.

9.1.5.2. Meningitis

For the further evaluation of the safety signal of meningitis in the investigational vaccine groups (AduFx, 2PedFx, PedFx, Adu2Fx, and Adu1Fx), all cases of meningitis occurring during the study will be reported as a SAE and clinical details of each case will be reported in a specific eCRF screen.

9.2. Events or outcomes not qualifying as adverse events or serious adverse events

9.2.1. Pregnancy

Female subjects who are pregnant or lactating at the time of vaccination must not receive additional doses of study vaccines but may continue other study procedures at the discretion of the investigator.

While pregnancy itself is not considered an AE or SAE, any adverse pregnancy outcome or complication or elective termination of a pregnancy for medical reasons will be recorded and reported as an AE or a SAE.

Note: The pregnancy itself should always be recorded on an electronic pregnancy report.

The following should always be considered as SAE and will be reported as described in Sections 9.4.1 and 9.4.3:

- Spontaneous pregnancy loss, including:
 - spontaneous abortion, (spontaneous pregnancy loss before/at 22 weeks of gestation)
 - ectopic and molar pregnancy
 - stillbirth (intrauterine death of fetus after 22 weeks of gestation).
- Note: the 22 weeks cut-off in gestational age is based on WHO-ICD 10 noted in the EMA Guideline on pregnancy exposure [EMA, 2006]. It is recognized that national regulations might be different.
- Any early neonatal death (i.e. death of a live born infant occurring within the first 7 days of life).
- Any congenital anomaly or birth defect (as per [CDC MACDP] guidelines) identified in the offspring of a study subject (either during pregnancy, at birth or later) regardless of whether the fetus is delivered dead or alive. This includes anomalies identified by prenatal ultrasound, amniocentesis or examination of the products of conception after elective or spontaneous abortion.

Furthermore, any SAE occurring as a result of a post-study pregnancy AND considered by the investigator to be reasonably related to the investigational vaccines will be reported to GSK Biologicals as described in Section 9.4.3. While the investigator is not obligated to actively seek this information from former study participants, he/she may learn of a pregnancy through spontaneous reporting.

9.3. Detecting and recording adverse events, serious adverse events and pregnancies

9.3.1. Time period for detecting and recording adverse events, serious adverse events and pregnancies

All AEs starting within 30 days following administration of each dose of study vaccines (Day 0 to Day 29) must be recorded into the appropriate section of the eCRF, irrespective of intensity or whether or not they are considered vaccination-related.

For vaccinated subjects, the time period for collecting and recording SAEs will begin at the first receipt of study vaccine (Day 0) and will end at the last study visit (Day 376). For the infectivity controls group, the time period for collecting and recording SAEs will begin on the first day of the sporozoite challenge (Day 286) and will end at the last study visit (Day 314). See Section 9.4 for instructions on reporting of SAEs.

All AEs/SAEs leading to withdrawal from the study will be collected and recorded from the time of the first receipt of study vaccines (Day 0) for AduFx, 2PedFx, PedFx, Adu2Fx, and Adu1Fx groups.

In addition to the above-mentioned reporting requirements and in order to fulfill international reporting obligations, SAEs that are related to study participation (i.e. protocol-mandated procedures, invasive tests, a change from existing therapy) or are related to a concurrent GSK medication/vaccine will be collected and recorded from the time the subject consents to participate (i.e. Screening) in the study until she/he is discharged from the study.

For vaccinated subjects, the time period for collecting and recording pregnancies will begin at the first receipt of study vaccines (Day 0) and will end at the last study visit (Day 376). For the infectivity controls group, the time period for collecting and recording pregnancies will begin on the first day of the sporozoite challenge (Day 286) and will end at the last study visit (Day 314). See section 9.4 for instructions on reporting of pregnancies.

For vaccinated subjects, the time period for collecting and recording of AEs of specific interest (meningitis and pIMDs) will begin at the first receipt of study vaccines (Day 0) and will end at the last study visit (Day 376). See section 9.4 for instructions on reporting of pIMDs.

An overview of the protocol-required reporting periods for AEs, SAEs and pregnancies is given in [Table 25](#), [Table 26](#) and [Table 27](#).

Table 25 Reporting periods for collecting safety information for the investigational vaccine groups: AduFx, 2PedFx, PedFx, and Adu2Fx)

Study visits	1	2	3	6	7	10	11 to 30	31
Study days	-90 to 0	0 6	28 34	58	196 202	226	286 314 315	376
Solicited local and general AEs post-vaccination		■	■		■			
Unsolicited AEs post-vaccination		■	■	■	■	■	■	
AEs post-challenge							■	
AEs and SAEs leading to withdrawal from further vaccination		■	■	■	■	■	■	■
SAEs (all, fatal, related)		■	■	■	■	■	■	■
SAEs related to study participation, or to a concurrent GSK medication/vaccine		■	■	■	■	■	■	■
AEs of specific interest (meningitis and pIMDs)		■	■	■	■	■	■	■
Pregnancies		■	■	■	■	■	■	■

Table 26 Reporting periods for collecting safety information for the investigational vaccine groups: Adu1Fx

Study visits	1	2	3	7	10	11 to 30	31
Study days	-90 to 0	0 6	28	196 202	226	286 314 315	376
Solicited local and general AEs post-vaccination		█		█			
Unsolicited AEs post-vaccination		█	█	█	█		
AEs post-challenge						█	
AEs and SAEs leading to withdrawal from further vaccination		█	█	█	█	█	█
SAEs (all, fatal, related)		█	█	█	█	█	█
SAEs related to study participation, or to a concurrent GSK medication/vaccine		█	█	█	█	█	█
AEs of specific interest (meningitis and pIMDs)		█	█	█	█	█	█
Pregnancies		█	█	█	█	█	█

Table 27 Reporting periods for collecting safety information for the infectivity control group

Study visits	1b	11 to 30		
Study days	258 to 286	286	314	315
AEs post-challenge				
SAEs (all, fatal, related)				
SAEs related to study participation, or to a concurrent GSK medication/vaccine				
Pregnancies				

9.3.2. Post-Study adverse events and serious adverse events

A post-study AE/SAE is defined as any event that occurs outside of the AE/SAE reporting period defined in [Table 25](#), [Table 26](#) and [Table 27](#). Investigators are not obligated to actively seek AEs or SAEs in former study participants. However, if the investigator learns of any SAE at any time after a subject has been discharged from the study, and he/she considers the event reasonably related to the investigational vaccines, the investigator will promptly notify the Study Contact for Reporting SAEs.

9.3.3. Evaluation of adverse events and serious adverse events**9.3.3.1. Active questioning to detect adverse events and serious adverse events**

As a consistent method of collecting AEs, the subject should be asked a non-leading question such as:

'Have you felt different in any way since receiving the vaccines or since the previous visit?'

When an AE/SAE occurs, it is the responsibility of the investigator to review all documentation (e.g. hospital progress notes, laboratory and diagnostics reports) relative to the event. The investigator will then record all relevant information regarding an AE/SAE in the eCRF. The investigator is not allowed to send photocopies of the subject's medical records to GSK Biologicals instead of appropriately completing the eCRF. However, there may be instances when copies of medical records for certain cases are requested by GSK Biologicals. In this instance, all subject identifiers will be blinded on the copies of the medical records prior to submission to GSK Biologicals.

The investigator will attempt to establish a diagnosis pertaining to the event based on signs, symptoms, and/or other clinical information. In such cases, the diagnosis should be documented as the AE/SAE and not the individual signs/symptoms.

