1.2.2. Rationale for the study design

This study is designed to evaluate efficacy, immunogenicity and safety of various dose schedules of GSK Biologicals' candidate malaria vaccines RTS,S/AS01_B (adult formulation containing 50 µg RTS,S antigen and AS01_B formulation with 50 µg of MPL and 50 µg of QS-21 per 0.5 ml) and RTS,S/AS01_E (pediatric formulation containing 25 µg RTS,S antigen and AS01_E formulation with 25 µg of MPL and 25 µg of QS-21 per 0.5 ml) in healthy malaria-naïve subjects aged 18-55 years. The study proposed herein will include six study groups. Four of these study groups will be vaccinated according to a 0, 1, 7-month schedule and one according to a 0, 7-month schedule. The immunization schedule of reference will be the same as the one used in study MALARIA-071 (117014), i.e. RTS,S/AS01_B full dose at Month 0 and Month 1 and RTS,S/AS01_B 1/5th dose at Month 7. Three months after the last dose of study vaccines, all subjects will undergo a sporozoite challenge and will be compared to an infectivity control group:

- **Group AduFx** will receive RTS,S/AS01_B full dose at Month 0 and Month 1 + RTS,S/AS01_B fractional dose (1/5th dose) at Month 7 (immunization schedule of reference).
- **Group 2PedFx** will receive double dose of RTS,S/AS01_E at Month 0 and Month 1 + double dose of RTS,S/AS01_E fractional dose (1/5th dose) at Month 7.
- **Group PedFx** will receive RTS,S/AS01_E full dose at Month 0 and Month 1 + RTS,S/AS01_E fractional dose (1/5th dose) at Month 7.
- **Group Adu2Fx** will receive RTS,S/AS01_B full dose at Month 0 + RTS,S/AS01_B fractional dose (1/5th dose) at Month 1 and Month 7.
- **Group Adu1Fx** will receive RTS,S/AS01_B full dose at Month 0 + RTS,S/AS01_B fractional dose (1/5th dose) at Month 7.
- **Group infectivity control** will not receive any immunization but will undergo the sporozoite challenge.

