5.2. Inclusion criteria for enrolment

Deviations from inclusion criteria are not allowed because they can potentially jeopardize the scientific integrity of the study, regulatory acceptability or subject safety. Therefore, adherence to the criteria as specified in the protocol is essential.

All subjects must satisfy ALL the following criteria at study entry:

- Subjects who, in the opinion of the investigator, can and will comply with the requirements of the protocol (e.g. completion of the diary cards, return for follow-up visits).
- Written informed consent obtained from the subject prior to performing of any study specific procedure.
- A male or female between, and including, 18 and 55 years of age at the time of enrolment.
- Healthy subjects as established by medical history and clinical examination before entering into the study.

- Available to participate for the duration of the study (approximately 16 months per vaccinated subject and approximately three months per subject in the infectivity control group).
- Female subjects of non-childbearing potential may be enrolled in the study.
 - Non-childbearing potential is defined as pre-menarche, current tubal ligation, hysterectomy, ovariectomy or post-menopause.

Please refer to the [glossary of terms](#) for the definition of menarche and menopause.

- Female subjects of childbearing potential may be enrolled in the study, if the subject:
 - has practiced adequate contraception for 30 days prior to vaccination, and
 - has a negative pregnancy test at enrolment, and
 - has agreed to continue adequate contraception during the entire treatment period and for two months after completion of the vaccination series and/or malaria challenge.

Please refer to the [glossary of terms](#) for the definition of adequate contraception.

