If infection does not develop within 18 days, the subject will be released from staying nightly at the hotel. Subjects who do not develop malaria will be required to come to the clinical center for evaluation and blood drawing for smears every two days up to 28 days post-challenge (Days 306 [Visit 26], 308 [Visit 27], 310 [Visit 28], 312 [Visit 29], and 314 [Visit 30]). A subject who develops malaria and has three consecutive (separated by more than 12 hours) negative smears following initial treatment may be excused from the remaining hotel visits and the late post-challenge clinic visits at Days 306, 308, 310, and 312 (20, 22, 24 and 26 days post-challenge), but will be required to come to the clinic center at Day 314 (28 days post-challenge [Visit 30]). Telephone contact will be made if the subject does not keep a scheduled follow-up appointment. Symptom screening via telephone may suffice in lieu of clinical visits for Days 306, 308, 310, or 312 which fall upon a weekend.

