It is anticipated that treatment of malaria will be curative, since relapses do not occur after adequate treatment of *P. falciparum* infections. No previous *P. falciparum* subject infected and treated by WRAIR has had a malaria relapse. Subjects will be advised to contact the study physician, or to advise their personal physician of their participation in this malaria study, if fever, headache, or other symptoms possibly related to malaria develop at any time within one year after completion of the study. In the unlikely event that malaria recurs, the subject will be retreated with chloroquine, atovaquone/proguanil (*Malarone*) standard oral dosage of 1 g/400 mg (four adult tablets per day for three consecutive days), or artemether/lumefantrine (*Coartem*) standard oral dosage of 80 mg/480 mg (four tablets initial dose, four tablets 8 hours later, and then four tablets twice daily for the following two days).

No human viruses are known to be transmitted by colonized *Anopheles* mosquitoes. Blood purchased for malaria feedings has been commercially tested using FDA-approved test methods for antibodies to HIV, HCV, and syphilis, as well as for the presence of HBsAg; all blood has tested negatively for these tests. No documented cases of HIV or viral hepatitis transmission from mosquitoes to humans have occurred. The risk of accidentally transmitting malaria to a person in the community will be negligible because:

- The infected mosquitoes will be raised in secure insectary at WRAIR.
- All malaria challenges occur in a secure insectary.
- The infected mosquitoes never leave the secured insectary area at any time.
- Malaria infections in subjects will be treated promptly before gametocytes can develop (generally ten days after the development of patent malaria), thus the risk of transmission to local mosquitoes is reduced.

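### After discharge a new SAE must be notified only if it is related to the vaccine, so for unvaccinated infectivity controls the rule can never apply

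*Protocol*

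**What the plan says.** Section 9.3.2 of the protocol defines a post-study event by reference to the reporting periods in Tables 25, 26 and 27. Table 27 is the infectivity-control table, so the section governs controls as well as vaccinees. Investigators need not look for events after discharge. If one learns of an SAE and "considers the event reasonably related to the investigational vaccines, the investigator will promptly notify the Study Contact for Reporting SAEs".

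Section 1.2.2 says that the control group "will not receive any immunization but will undergo the sporozoite challenge". Under Section 9.3.1 the control SAE period runs from Day 286 to the last visit at Day 314, and Table 8 places their study conclusion at that visit (Visit 30). Section 9.3.1 also collects SAEs related to study participation, including protocol-mandated procedures, but only from consent until discharge.

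Section 6.4.1.6 advises subjects to contact the study physician, or to tell their own physician that they took part, "if fever, headache, or other symptoms possibly related to malaria develop at any time within one year after completion of the study".

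**The concern.** The intervention that every subject shares is the sporozoite challenge, not the vaccine. The post-study rule is written for a vaccine trial and names only the vaccine as a possible cause. A control admitted to hospital with late or recurrent malaria after Day 314 would have an SAE with an obvious link to the study. The protocol's advice could bring it to the study physician, and Section 9.3.2 would still not ask for it to be notified. In a vaccinee after Day 376, the same holds for an SAE put down to the challenge or to the antimalarial drug.

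At stake is whether the sponsor is sure to hear of rare, late, serious harm from a procedure that exposes healthy volunteers to malaria.

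**Working it through.** There is little arithmetic. The question is whether any rule other than 9.3.2 captures a new, challenge-related SAE after discharge.

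**Days (protocol Tables 8, 9 and 11; Sections 6.4.1.6 and 9.3.1)**
- Challenge to the controls' last visit: 314 − 286 = 28 days, which matches the plan's own figure.
- With the ±7-day allowance on Visit 30: 28 − 7 = 21 to 28 + 7 = 35 days.
- Challenge to the vaccinees' last visit: 376 − 286 = 90 days.
- The one-year advice starts at study completion. For a control it nominally runs from Day 314 to Day 314 + 365 = 679, and all of it lies outside the SAE collection period.

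**Rules that might apply to a new SAE in a control after Day 314**
- *9.3.1, general SAE collection:* ends at Day 314. Does not apply.
- *9.3.1, SAEs related to study participation:* would fit the challenge, but ends at discharge. Does not apply.
- *9.4.1, prompt reporting:* limited to SAEs within the Section 9.3 period. Does not apply.
- *9.3.2, post-study SAEs:* requires relatedness to the vaccine. Without vaccine exposure this cannot be met.
- *9.2.1, SAEs from a post-study pregnancy:* has the same vaccine-only condition. Cannot be met.
- *9.5.1.2, follow-up after discharge:* follows SAEs until they resolve and passes on new information about those already reported. It does not cover a new event.
- *9.5.2, pregnancy outcome:* an outcome that is an SAE is always reported, whatever the reporting period. This is the one exception.

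**Vaccinees after Day 376**
The condition can be met if the investigator suspects the vaccine. It is not met when the SAE is attributed to the challenge or the antimalarial treatment alone.

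**Causality assessment**
The question in Section 9.3.3.2.2 asks only about the investigational vaccine. The same section's list of contributing factors to an SAE does include a procedure required by the protocol. So attribution to the challenge can already be recorded. What is missing is the link from that attribution to a post-study notification.

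**The case against.** **Late events are unlikely.** Section 6.4.1.6 expects treatment to be curative, says relapse does not follow adequate treatment, reports none in subjects previously infected and treated at WRAIR, and calls recurrence unlikely. Section 6.4.1.5 gives 25 days as the longest reported pre-patent period, inside the nominal 28 days. The one-year advice is a precaution, not a forecast, and it is not an instruction to report, since telling one's own physician satisfies it. All of this stands. It limits the importance of the point but does not explain why vaccine-related events are notifiable after discharge and challenge-related ones are not.

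**Other duties may exist.** Section 6.1 binds the study to GCP and applicable regulation. A reader might infer from 9.3.2 that a late SAE in a control carries no reporting duty of any kind. The documents do not support that. They show only that this section does not require notification of the sponsor's contact. Section 6.4.1.6 also provides for retreatment, so care is not in question.

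**The safety tables are untouched.** A reader might infer that the challenge would look safer than it is. This does not follow. Protocol Section 11.2.3 and SAP Sections 4.2.3 and 6.5.1 fix the challenge windows: AEs for 30 days after challenge, and SAEs from Day 286 to Day 314. A post-study notification falls outside them under the present wording and under the amended one.

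**Pregnancy.** Contraception is required "for two months after completion of the vaccination series and/or malaria challenge", while pregnancy recording in controls stops at Day 314. A reader might call this a contradiction and ask for longer recording. The two periods serve different purposes, a test is done before challenge, and Section 9.5.2 already captures outcomes that are SAEs. Longer recording would mean contact with controls after their study conclusion. Whether that is worthwhile is a debatable design choice, not an error in the plan.

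**Conclusion.** The point holds as a gap in one stated rule. For all 20 to 30 infectivity controls, Section 9.3.2 can never require notification of a new SAE after they leave, nominally 28 days after challenge, apart from the pregnancy outcomes in Section 9.5.2. In vaccinees it leaves out post-study SAEs attributed to the challenge or the antimalarial treatment and not to the vaccine.

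The practical size is small. Few events are expected, and no endpoint, analysis set or planned table changes. The gap is in notification of the sponsor only. It merits correction because challenged volunteers should be covered by the same passive safety net as vaccinated ones, and because the change costs almost nothing.

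The conclusion assumes that relatedness to the vaccine is read literally, and that no document outside the protocol and SAP already requires notification of late challenge-related SAEs. Consent and agreement pages were not available to check.

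**What to change.** In Section 9.3.2, widen the condition so that it reads: *reasonably related to the investigational vaccines, the sporozoite challenge, the antimalarial treatment or other study procedures*. Make the same change in the sentence of Section 9.2.1 on SAEs arising from a post-study pregnancy, so that the two rules agree.

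Reporting stays passive: the investigator notifies what he or she happens to learn and is not asked to look for events. The edit adds no visit, call, sample or table, and it leaves the control reporting periods in Section 9.3.1 and Table 27 as they are. The cost is one phrase in two places and, at most, an occasional additional report.
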